11.5 OTHER SAFETY PARAMETERS

11.5.1 Columbia-Suicide Severity Rating Scale

For the Columbia-Suicide Severity Rating Scale (C-SSRS), the number and percentage of participants with suicidal ideation and suicidal behavior before the double-blind treatment period and during double-blind treatment and safety follow-up periods will be summarized by treatment group for the Safety population. Supportive tabular display of participants with all values will be provided, including study center, PID number, treatment group, visit number, intensity of suicidal ideation, suicidal behavior type, and lethality of suicidal behavior.

11.5.2 Potential Hy's Law

Potential Hy's Law criteria within a 24 hours window is defined by a post baseline elevation of alanine aminotransferase (ALT) or aspartate aminotransferase (AST) $\geq 3x$ ULN, along with total bilirubin (TBL) $\geq 2x$ ULN and a non-elevated alkaline phosphatase (ALP) $< 2x$ ULN, all based on blood draws collected within a 24 hour period.

Potential Hy's Law criteria without time window (e-DISH) is defined by maximum of post baseline elevation of ALT or AST $\geq 3x$ ULN, along with maximum of post baseline elevation of TBL $\geq 2x$ ULN.

Participants who meet the potential Hy's Law criteria from the first dose of study drug to within 30 days after the last dose of study treatment will be summarized. Supportive tabular displays will also be provided.

11.5.3 Brief Psychiatric Rating Scale—Positive Symptoms Subscale

The BPRS+ total score is defined as the sum of 4 positive individual scores including conceptual disorganization, suspiciousness, hallucinatory behavior, and unusual thought content. Each question is presented on a 7-point Likert scale with a choice for NA as not assessed. If any item were not observed, not assessed, or missing, then the total score was missing.

Descriptive statistics of actual values at baseline, post baseline, and change from baseline for BPRS+ total score as well as for 4 positive individual scores will be presented by

treatment group. Plots of mean values and their standard errors for the BPRS+ total score will be presented by treatment group and by visit for Safety population.

A participant will be considered to have a treatment-emergent symptom in the BPRS scale if any of the following BPRS items scores are ≤ 2 at baseline and > 2 after baseline: conceptual disorganization, suspiciousness, hallucinatory behavior, or unusual thought content. The number and percentage of participants reporting treatment-emergent symptoms in the BPRS scale will be tabulated for each individual item and for all 4 items specified above.

Listings of participants with treatment-emergent symptoms will be provided and will include the participant identification number and baseline and postbaseline values. Listings of all adverse events occurring in participants who have treatment-emergent symptoms will also be provided.

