12.9. Appendix 9: Clinical Global Impressions—Severity

SEVERITY OF ILLNESS

Considering your total clinical experience with this population, how mentally ill is the patient at this time? (Check one)

- 1 Normal, not at all ill
- 2 Borderline ill
- 3 Mildly ill
- 4 Moderately ill
- 5 Markedly ill
- 6 Severely ill
- 7 Among the most extremely ill patients

12.10. Appendix 10: Brief Psychiatric Rating Scale – Positive Symptoms Subscale**4-Item Positive Symptom Rating Scale***

NA = not able to be assessed, 1 = symptom not present, 6/7 = severe/extremely severe

1. Suspiciousness	NA	1	2	3	4	5	6	7
2. Unusual Thought Content	NA	1	2	3	4	5	6	7
3. Hallucinations	NA	1	2	3	4	5	6	7
4. Conceptual Disorganization	NA	1	2	3	4	5	6	7

SCORE: _____

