11.1 ADVERSE EVENTS

Adverse events will be coded by system organ class and preferred term using the *Medical Dictionary for Regulatory Activities* (MedDRA), version 22.0.

An AE will be considered a treatment-emergent adverse event (TEAE) if the AE began or worsened (increased in severity or became serious) on or after the date of the first dose of study medication. However, an AE that occurs more than 30 days after the last dose of study medication will not be counted as a TEAE. Per case report form instructions, a new AE record will be created with a new AE onset date for any AE that worsens. Therefore TEAEs can simply be identified as those AEs with recorded onset date on or after the date of the first dose of study intervention and within 30 days after the last dose of study intervention.

The number and percentage of participants reporting TEAEs in each treatment group will be summarized overall and weekly. The number and percentage of participants reporting TEAEs in each treatment group will be tabulated by descending percentage in any group, by system organ class and preferred term, and further categorized by severity and causal relationship to the study treatment. If more than 1 AE is coded to the same preferred term for the same patient, the patient will be counted only once for that preferred term using the greatest severity and strictest causality for the summarization by severity and causal relationship.

The total number of TEAEs by system organ class and preferred term; system organ class, preferred term, and severity; system organ class, preferred term, and causal relationship to the study treatment will be summarized by treatment group.

The incidence of common ($\geq 2\%$ of participants in any treatment group) TEAEs will be summarized by preferred term and treatment group and sorted by decreasing frequency for the test treatment highest dose. It will be reported for Safety population overall.

The number and percentage of participants in the Safety Population who have AEs leading to premature discontinuation of the study treatment will be summarized by preferred term and treatment.

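### The BPRS+ treatment-emergent rule cannot flag an item already above 2 at baseline, so worsening confined to such an item is left out of the treatment-emergent count and its two listings

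*SAP*

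**What the plan says.** The rule is in SAP 11.5.3 (Part A). It opens "A participant will be considered to have a treatment-emergent symptom in the BPRS scale if any of the following" and sets the condition that "BPRS items scores are ≤ 2 at baseline and > 2 after baseline", applied to conceptual disorganization, suspiciousness, hallucinatory behavior and unusual thought content. Protocol Appendix 10 gives the item anchors: "NA = not able to be assessed, 1 = symptom not present, 6/7 = severe/extremely severe".

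Three outputs use this flag:
- the tabulation: "The number and percentage of participants reporting treatment-emergent symptoms in the BPRS scale will be tabulated for each individual item", and also for the four items together;
- the participant listing: "Listings of participants with treatment-emergent symptoms will be provided";
- the AE display: "Listings of all adverse events occurring in participants who have treatment-emergent symptoms will also be provided".

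The section states no denominator for the percentages. SAP 11.0 takes the last nonmissing predose assessment as baseline. The Part A schedule (Protocol 2.1, SAP Table 4-1) has BPRS+ at Screening and then not until Visit 3, so the baseline will normally be the Screening score, up to 14 days before dosing.

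For adverse events, SAP 11.1 uses a wider idea of treatment-emergent: an event qualifies if "the AE began or worsened (increased in severity or became serious) on or after the date of the first dose".

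**The concern.** The rule captures symptoms that cross a threshold and has no place for a symptom that was already over it and became worse. Under the AE definition in the same SAP, worsening counts; under the BPRS+ definition it does not. The laboratory and ECG sections (SAP 11.2 and 11.4) also count only new abnormalities, but they limit the denominator to participants who were not abnormal at baseline, and 11.4 separately tabulates the size of QTc increases. The BPRS+ section does neither.

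BPRS+ is the measure of psychotomimetic effects named in the protocol's objectives, and the protocol sets this drug against ketamine on exactly that kind of effect. The treatment-emergent tabulation and its listings are the dedicated BPRS+ displays that count individual participants and link them to their AEs. An incomplete flag makes those displays incomplete in the same way.

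**Working it through.** There is no planned figure to reproduce. The check applies the SAP rule to every possible upward move of one item.

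**Inputs.** Item range 1 to 7 (SAP 11.5.3; Protocol Appendix 10). Flag: baseline ≤ 2 and postbaseline > 2 (SAP 11.5.3). About 25 participants per arm (SAP 14.0).

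**1. Moves flagged and missed.**
- Upward moves on a 7-point item: 7 × 6 / 2 = 21.
- Flagged: 2 baseline values (1, 2) × 5 postbaseline values (3 to 7) = 10.
- Missed: 21 − 10 = 11. One is 1 to 2. The other 5 × 4 / 2 = 10 start at 3 or more: 3 to 4, 5, 6 or 7; 4 to 5, 6 or 7; 5 to 6 or 7; 6 to 7.
- So 2 to 3 is flagged and 3 to 6 is not.

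**2. Item level and participant level.**
- One item goes 3 to 6 and the other three stay at 1: the participant is not flagged.
- One item goes 3 to 6 and another goes 1 to 3: the participant is flagged through the second item, but the 3 to 6 item still adds nothing to its own per-item count.

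**3. Can a baseline item exceed 2?** Protocol 6.2 excludes lifetime psychotic disorder and MDD with psychotic features. Neither 6.1 nor 6.2 sets a BPRS+ limit, so such a score is allowed. Because the baseline is normally from Screening, an item scored 3 there that settled before Day 1 and then reached 6 on treatment would also go unflagged.

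**4. Size.**
- One participant in an arm: 1/25 = 4 percentage points.
- The same 3 to 6 change moves that item's arm mean by (6 − 3)/25 = 0.12 points.
- The documents do not say how often a baseline item exceeds 2. If a proportion q of participants have one, P(at least one in an arm of 25) = 1 − (1 − q)^25:

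| q (assumed) | P(at least one in 25) |
|---|---|
| 0% | 0% |
| 1% | 22% |
| 2% | 40% |
| 5% | 72% |
| 10% | 93% |

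- Denominator: if 2 of 25 start above 2 on an item and one of the other 23 crosses, the rate is 1/25 = 4.0% over everyone and 1/23 = 4.3% over those who could cross.

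**5. With a worsening category.** Adding baseline > 2 with any postbaseline score above that baseline flags 10 + 10 = 20 of the 21 moves. Only 1 to 2 remains unflagged.

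**The case against.** The case for leaving the rule alone has several parts.

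- **Any item suffices.** A reader might infer that everyone who goes from 3 to 6 on an item drops out of all three outputs. The rule does not say that: such a participant still appears if any other item crosses from 2 or below. This limit stands.
- **The data are kept.** A reader might also infer that the worsening disappears from the report. It does not. SAP 11.5.3 summarizes change from baseline for each item and 11.0 requires the maximum, so a 3-point rise would show as the arm's largest unless someone changed more. SAP 16.3 puts all assessments in the data listings, and 11.1 lists all AEs by participant. This stands too. What those outputs lack is a count of who worsened and a link from that group to its AEs.
- **There is an AE route.** Protocol Appendix 4 treats exacerbation of a pre-existing condition as an AE, and the TEAE rule would count it. That is a real safeguard, but it depends on the change being recorded as an AE; the rating scale is there as a separate measure.
- **Counting new abnormalities only is this SAP's habit.** True for laboratory and ECG values, and a defensible choice. But those sections pair it with a matching denominator, and this one does not.
- **The group may be empty.** The exclusions make raised baseline items uncommon, and the documents give no frequency. This limits the size of the point, not its logic.
- **Noise.** One-point rises from 3 or more would be counted. The present rule already counts 2 to 3, and a separate row keeps the two kinds of change apart.

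Protocol 10.3.5.5 asks only for descriptive statistics on the BPRS+ total, so this display is an SAP addition with no test or decision attached to it.

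**Conclusion.** The point holds as a gap in one descriptive safety display. An item above 2 at baseline can never be flagged, however far it rises, and a participant whose only worsening is in such an item is missing from the treatment-emergent count, its listing and the linked AE listing. The reading of the rule needs no assumption.

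The size does rest on one. The number of participants with a baseline item above 2 is not in the documents and could be zero; the range of 0 to 10% used above is illustrative. Each affected participant is 4 percentage points in an arm of 25, while the denominator effect in the example is about 0.3 points.

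It would go too far to conclude that a psychotomimetic signal would be hidden, or that participants with pre-existing low-grade symptoms are the ones most at risk. The documents support neither: the scores and AEs remain available elsewhere, and no source is given for a higher risk. This is a cheap improvement to a named safety measure, not a flaw that threatens the trial's conclusions.

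**What to change.** Amend SAP 11.5.3 before database lock, for each of the four items:

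- **New:** baseline ≤ 2 and any postbaseline score > 2. Denominator: participants with baseline ≤ 2 and at least one postbaseline score for that item.
- **Worsened:** baseline > 2 and any postbaseline score above that item's own baseline. Denominator: participants with baseline > 2 and at least one postbaseline score for that item.
- **Combined:** either of these. Denominator: all participants with a baseline and at least one postbaseline score for that item.

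For the row covering all four items, flag a participant if any item is new or worsened. One person can be new on one item and worsened on another, so the combined count there need not equal the sum of the two. Build the participant listing and the AE display from the combined flag.

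The cost is a few sentences of SAP text and a small programming change, with no new data or visits. The number counted under the present rule is preserved as the 'new' row, over its proper denominator. The downside is that some one-point rises from a baseline of 3 or more will be counted; they appear separately under 'worsened', so a reader can discount them.

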11.5.4 Clinician Administered Dissociative States Scale

CADSS total score is defined as of 23 non-negative individual scores. Each question is presented on a 5-point Likert scale with 0 meaning “not at all” and 4 meaning “extreme”. If more than 4 items were missing, then the total score was set to missing; if there were 4 or fewer items missing, then the total score is set to the sum of non-missing items multiplied by the total number of items divided by the number of non-missing items.

Descriptive statistics of actual values at baseline, post baseline, and change from baseline for CADSS total score will be presented by treatment group at each assessment timepoint. Plots of mean values and their standard errors for the CADSS total score will be presented by treatment group and by visit for Safety population.

11.5.5 The Hamilton Anxiety Rating Scale

The HAM-A is a clinician-rated scale to rate the severity of anxiety symptoms. The participant tested over 14-questions, and rated on a scale from 0 to 4, with 1 indicating a “not present” response and 4 indicating a “severe” response. The HAM-A will be administered by the investigator or a sub-investigator with extensive professional training and experience in assessing mental illness and qualification standards set by the sponsor and rater training vendor.

The exploratory analysis of HAM-A scores will be performed using the safety population for the double-blind treatment period and for the safety follow-up period, if applicable, P.

The exploratory parameters will include change from baseline in HAM-A total scores at Day 2, 8, and 15. Descriptive statistics of actual values at baseline, post baseline, and change from baseline for HAM-A total score will be presented by treatment group at each assessment timepoint.

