4.1. Part A

The primary objective of Part A is to evaluate the efficacy, as measured by improvement in MADRS total score, at 1 day after the initial single oral dose of AGN-241751 compared with placebo in participants with MDD (Day 1 [predose, defined as baseline] vs Day 2). The key secondary objectives are to evaluate the efficacy at Day 8, at Day 9 after single oral dose, at Day 15 after repeated dose, and at Day 22, 7 days after the completion of AGN-241751 dosing, when administered orally once daily compared with placebo in participants with MDD.

Objectives	Endpoints
Primary	

 To evaluate the efficacy at 1 day post the initial single oral dose of AGN-241751 compared with placebo in participants with MDD 	
 Change from baseline (Day 1, predose) in MADRS total score at 1 day after the first dose of treatment (Day 2)
Key Secondary	

 To evaluate the efficacy at Day 8, at Day 9 (single dose), at Day 15 (repeated dose) of AGN-241751 administered orally once daily, and at Day 22 (7 days after completion of AGN-241751 dosing) compared with placebo in participants with MDD 	
 Change from baseline (Day 1, predose) in MADRS total score at Day 8, Day 9, Day 15, and Day 22
Additional	

 Additional endpoint to be explored to determine differences between AGN-241751 and placebo in participants with MDD 	
 Change from baseline in CGI-S total score at Day 2, Day 8, Day 9, and Day 15 Rate of responders on MADRS or CGI S at Day 2, Day 8, Day 9, Day 15, and Day 22 Rate of remitters on MADRS at Day 2, Day 8, Day 9, Day 15, and Day 22 Time to first response on MADRS Time to first remission on MADRS Change from baseline (Day 1, predose) in HAM-A at Day 2, Day 8, and Day 15

Objectives	Endpoints

 Safety Measures 	
 AE recording, clinical laboratory measures, vital sign parameters, ECGs, and physical examinations Measure of psychotomimetic effects: BPRS+ Measure of dissociative effects: CADSS Measure of suicidality: C-SSRS

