10.3.2. Exploratory Analyses

10.3.2.1. Part A

The exploratory analyses of HAM-A scores will be performed using the safety population for the double-blind treatment period and for the safety follow-up period, if applicable, and will be fully defined in the SAP. The exploratory parameters will include change from baseline in HAM-A scores Day 2, Day 8, and Day 15. At Visit 2, the HAM-A will be administered with a look-back timeframe of 1 week. At all other evaluations, the HAM-A will be administered with a look-back timeframe of “since last evaluation.” The HAM-A will be collected only from participants entering the study after the amendment has been IRB approved.

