10.3 ADDITIONAL EFFICACY PARAMETERS

Additional efficacy parameters are as follows:

- Change from baseline in Clinical Global Impressions-Severity (CGI-S) at Day 2 (1 day after first dose), Day 8, Day 9 and Day 15
- MADRS responder status at Day 2 (1 day after first dose), Day 8, Day 9, Day 15 and Day 22
- CGI-S responder status at Day 2 (1 day after first dose), Day 8, Day 9 and Day 15
- MADRS remitter status at Day 2 (1 day after first dose), Day 8, Day 9, Day 15 and Day 22
- Time to first response
- Time to first remission

Analysis of change from baseline in CGI-S score will be performed using a similar MMRM to that used for the key secondary parameter. Multiple comparison procedure will not be applied to the above additional efficacy parameters.

Plots of fitted (least squares) mean values and their standard errors based on the MMRM model for the change from baseline in MADRS total score and in CGI-S score, respectively, will be presented by treatment group and by visit.

CGI-S responder is defined as participants achieving a score of ≤ 2 on the CGI-S of Illness scale.

During the randomized treatment period, 2 types of events for MADRS total score will be defined based on the following criteria:

- Responder: $\geq 50\%$ reduction from baseline MADRS total score
- Remitter: MADRS total score ≤ 10

Rates of responders and remitters will be reported by treatment group for each timepoint (Days 2, 8, 9, 15, and 22 after first dose of randomized treatment). A logistic regression model with LOCF imputation will be used to model the probability of a response or the probability of a remission as a function of a treatment group and baseline MADRS or CGI-S total score. The LOCF approach will be used to impute missing postbaseline values, provided that at least 1 postbaseline assessment is available. Missing values between the baseline and the first nonmissing postbaseline will be imputed with the baseline value. If all the postbaseline values are missing, the baseline value will not be carried forward. Only the total score of a parameter will be imputed using the LOCF approach; individual item scores will not be carried forward. Bar charts for the rates of responders and remitters in MADRS total score will be presented by treatment group and by study day.

Descriptive statistics for the first three additional endpoints and their associated statistical testing results from the MMRM models and logistic regression will be respectively presented by visit.

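### SAP 11.5.5 plans no drug–placebo estimate or baseline adjustment for HAM-A, an exploratory endpoint that the protocol sets up to look for differences from placebo (minor)

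*SAP*

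**What the plan says.** **Protocol.** Section 4.1 gives the endpoint as "Change from baseline (Day 1, predose) in HAM-A at Day 2, Day 8, and Day 15". The objective beside it reads "Additional endpoint to be explored to determine differences between AGN-241751 and placebo in participants with MDD". Section 9.1.4 describes HAM-A among the efficacy assessments. The additional efficacy parameters in 10.3.1.3.1 do not include it. It appears in 10.3.2.1 as an exploratory analysis, "The exploratory analyses of HAM-A scores will be performed using the safety population for the double-blind treatment period", with the method left to the SAP.

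**SAP.** HAM-A is absent from 10.3 and is handled in 11.5.5, among the other safety parameters: "The exploratory analysis of HAM-A scores will be performed using the safety population for the double-blind treatment period". The analysis itself is "Descriptive statistics of actual values at baseline, post baseline, and change from baseline for HAM-A total score will be presented by treatment group", at each timepoint. Section 6.2 groups the safety population by treatment received.

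**Comparator within the same tier.** For CGI-S, SAP 10.3 states "Analysis of change from baseline in CGI-S score will be performed using a similar MMRM to that used for the key secondary parameter". That model, in SAP 10.2, carries baseline and its interaction with visit, and SAP 10.0 runs it in mITT.

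**Data available.** Under the schedule of activities, HAM-A is taken predose at Visits 2, 3, 4 and 6/ET, so a Day 1 baseline exists. It is collected only from participants who enter after IRB approval of the amendment. The planned size is about 25 per arm in four arms, not based on power (SAP 14.0).

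**The concern.** The objective is about a difference between drug and placebo, and the plan for this endpoint stops at arm-level summaries. No contrast, interval or model is prespecified. Anyone reporting the anxiety result must therefore choose the comparison after the data are seen, or compare arm means by eye.

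CGI-S change serves the same objective, is measured at every HAM-A visit and gets a baseline-adjusted model. Neither document says why HAM-A is treated differently.

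There is also a cost in precision. Subtracting baseline does not remove a chance imbalance. If two arms differ by d at baseline, then with equal variances and correlation rho the expected change-score contrast is still shifted by (rho − 1)d. Using baseline as a covariate removes that shift under the linear model.

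**Working it through.** The documents state no effect size, SD, correlation or precision for HAM-A, so there is no figure of theirs to reproduce. The check has two parts.

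**1. Does any section supply a comparison for HAM-A?**

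| Item | HAM-A change | CGI-S change |
|---|---|---|
| Objective (Protocol 4.1) | additional, exploratory | additional, exploratory |
| Baseline collected | yes, Visit 2 predose | yes, Visit 2 |
| Population | safety (Protocol 10.3.2.1, SAP 11.5.5) | mITT (SAP 10.0) |
| Model | none | MMRM (SAP 10.3) |
| Baseline as covariate | no | yes, with visit interaction |
| Drug–placebo estimate and interval | none | from the MMRM |

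No other section fills the HAM-A column.

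**2. What would a baseline covariate be worth?**

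At one visit, let n be the number per arm, 1 the follow-up SD, k the ratio of baseline SD to follow-up SD, and rho the baseline–follow-up correlation. The values of k and rho are assumptions. In large samples:

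- Variance of a difference in mean change: (2/n)(1 + k² − 2·rho·k)
- Variance of a baseline-adjusted difference: (2/n)(1 − rho²)
- The first bracket minus the second is (k − rho)², so adjustment is never less precise.

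With equal variances (k = 1) the variance ratio, adjusted over change, is (1 − rho²)/(2(1 − rho)) = (1 + rho)/2.

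| rho | variance ratio | SE ratio | SE reduction | equivalent sample |
|---|---|---|---|---|
| 0.3 | 0.65 | 0.806 | 19% | 1.54× |
| 0.5 | 0.75 | 0.866 | 13% | 1.33× |
| 0.7 | 0.85 | 0.922 | 8% | 1.18× |
| 0.9 | 0.95 | 0.975 | 2.5% | 1.05× |

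For scale, at n = 25 and rho = 0.5 the change-score SE is √(2/25) × √(2 × 0.5) = 0.283 SD. The adjusted SE is √(2/25) × √(1 − 0.25) = 0.245 SD. The 95% half-widths are about 1.96 × 0.283 = 0.55 SD and 1.96 × 0.245 = 0.48 SD.

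Simulating four arms gave SE ratios of 0.82, 0.87 and 0.96 at 25 per arm and 0.81, 0.87 and 0.96 at 10 per arm, for rho of 0.3, 0.5 and 0.8. The formula gives 0.81, 0.87 and 0.95.

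**Unequal variances.** The gain shrinks as k falls from 1 towards rho and vanishes at k = rho. At rho = 0.5 and k = 0.7, the change bracket is 1 + 0.49 − 0.70 = 0.79 and the variance ratio is 0.75/0.79 = 0.95, worth about 5% more participants instead of 33%. At k = 0.5 the bracket is 1 + 0.25 − 0.50 = 0.75 and the gain is zero. A larger follow-up variance therefore usually reduces the benefit. The exception is k below 2·rho − 1, which matters only at high correlation (k below 0.8 at rho = 0.9).

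**The case against.** The best defence is that the SAP follows the protocol. Protocol 10.3.2.1 makes HAM-A exploratory and names the safety population, and the efficacy lists of both documents leave it out. A descriptive summary is a common choice for an exploratory endpoint in a study that is not sized on power. This stands. A reader might infer that the SAP moved HAM-A into an as-treated population on its own authority; the documents do not support that. As-treated grouping changes the comparison only if someone receives the wrong treatment, and it has no bearing on precision.

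A reader might also infer that the plan cannot address its own objective. That goes too far. SAP 11.0 provides n, mean and SD for continuous variables, and SAP 11.5.5 applies descriptive statistics to change as well as to actual values. An unadjusted difference with an interval can be derived from that table, and baseline is subtracted even though it is not a covariate.

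The post-amendment restriction suggests arms below 25 for HAM-A, but neither document says how many participants entered earlier. Smaller arms are likely, not established.

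Finally, the remedy has costs. SAP 10.0 pools centres on mITT counts, so some pooled centres may lack HAM-A data in an arm.

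None of this provides the missing comparison. It limits how much weight the point can bear.

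**Conclusion.** The point holds as a minor one. HAM-A change is an exploratory endpoint meant to look for differences from placebo, and the SAP specifies no difference, interval or baseline-covariate adjustment for it, while CGI-S in the same tier gets all three. The missing prespecified contrast matters more than the precision.

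The precision gain is moderate at best: a standard error 19% to 2.5% smaller for rho from 0.3 to 0.9, relative to a change-score comparison that the SAP does not itself plan. It rests on assumed correlations, equal variances and large-sample formulas. The gain may be close to zero if follow-up scores are much more variable than baseline scores at moderate correlation. No primary, secondary or safety conclusion depends on it.

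**What to change.** In SAP 11.5.5:

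- Keep the descriptive table.
- Add an exploratory MMRM of HAM-A change at Days 2, 8 and 15 with treatment, visit, treatment-by-visit, baseline HAM-A and baseline-by-visit.
- Group by randomised treatment, in participants with a baseline and at least one post-baseline HAM-A.
- Use the covariance fallback order of SAP 10.1. If pooled centre is included, re-pool it or drop it where cells are sparse in the HAM-A subset.
- Report LS mean differences from placebo with nominal 95% CIs, labelled exploratory.
- Record the addition in SAP 17.0, which now lists no changes.

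SAP 16.2 has no HAM-A total-score or missing-item rule, so one should be added; the descriptive table needs it too.

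The cost is SAP wording, one extra exploratory table and reuse of a model already planned. It brings a small departure from the population and grouping in Protocol 10.3.2.1, and the model may need simplifying if the post-amendment subset is small. No new data or visits are needed.
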